#### 13.6 Accrual Time and Study Duration

The anticipated accrual rate is approximately 7 patients per month, based on our most-recent previous male hot flash trial (conducted 15 years ago to evaluate gabapentin) and recent survey information. Therefore, the accrual period for this phase II trial is expected to be 13 months. The final analysis is predicted to begin approximately 15 months after the trial begins (i.e., as soon as the last patient has been observed for 6 weeks).

#### 13.7 Data and Safety Monitoring

The study chair(s) and the study statistician will review the study at regular intervals to identify accrual and adverse events. The Alliance Data Safety Monitoring Board (DSMB) is responsible for reviewing accrual and safety data for this trial at least twice a year, based on reports provided by the Alliance Statistics and Data Management Center (SDMC).

Required submission of patient demographic data for this study will be submitted automatically via OPEN.

Note: Serious adverse events must be submitted via CTEP-AERS per protocol guidelines.

#### **13.7.1** Adverse Event Stopping Rules

The stopping rules specified below are based on the knowledge available at study development. We note that the adverse event stopping rule may be adjusted in the event of either (1) the study re-opening to accrual or (2) at any time during the conduct of the trial and in consideration of newly acquired information regarding the adverse event profile of the treatment(s) under investigation. The study team may choose to suspend accrual because of unexpected adverse event profiles that have not crossed the specified rule below.

Accrual will be temporarily suspended to this study if at any time we observe adverse events considered at least possibly related to study treatment (i.e., an adverse event with attribute specified as "possible", "probable", or "definite") that satisfy either of the following:

- if 2 or more patients in the first 10 treated patients experience a grade 3 or higher adverse event felt to be attributed to the study agent and the event rate is higher in the treatment arms than the placebo arm.
- if after the first 10 patients have been treated, 10% of all patients experience a grade 3 or higher adverse event felt to be attributed to the study agent and the event rate is higher in the treatment arms than the placebo arm.

We note that we will review grade 4 and 5 adverse events deemed "unrelated" or "unlikely to be related," to verify their attribution and to monitor the emergence of a previously unrecognized treatment-related adverse event.

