#### 2.2 Secondary objectives

- **2.2.1** To assess study accrual rates and compliance with the therapy.
- **2.2.2** To characterize the safety and adverse event profile of two doses of oxybutynin in the study population.
- **2.2.3** To evaluate the consistency of the results across the various methods used to evaluate the efficacy of oxybutynin (i.e., hot flash scores versus hot flash frequencies, mean differences versus 50% or greater reduction since baseline, single day versus full week to define patients' baseline hot flash scores).
- **2.2.4** To compare patient-reported quality of life and hot flash interference, as measured by the HFRDIS, across arms.
- **2.2.5** To compare other changes in patient symptoms, as measured by the Symptom Experience Questionnaire, across arms.

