#### 13.2 Study Design

Patients will be randomly assigned to oxybutynin at 2.5 mL twice daily, oxybutynin at 5.0 mL twice daily, placebo at 2.5 mL twice daily, or placebo at 5.0 ml twice daily in a 2:2:1:1 ratio according to the dynamic allocation scheme. Stratification factors will include daily hot flash frequency at baseline (4 to 9 hot flashes per day versus 10 or more hot flashes per day), hot flash duration at baseline (less than 9 months versus 9 or more months), and number of prior hot flash therapies (0 versus 1 or more). The study design includes two placebo arms to match the dose of the two oxybutynin arms; however, patients randomized to the two placebo arms will be combined to form a single placebo arm for analysis. All analyses will follow an intent-to-treat approach that includes all randomized patients who meet eligibility criteria.

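### The adverse-event suspension rule in Section 13.7.1 pools both oxybutynin doses and counts placebo men in its denominator, so events confined to the 5 mL arm meet the 10% limit only at an observed rate of about 30% in that arm

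*Combined protocol and SAP*

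**What the plan says.** Section 13.7.1 has two limbs.

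- Early limb: accrual pauses "if 2 or more patients in the first 10 treated patients experience a grade 3 or higher adverse event".
- Later limb: it pauses "if after the first 10 patients have been treated, 10% of all patients experience a grade 3 or higher adverse event".

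Both limbs are restricted to "adverse events considered at least possibly related to study treatment", and both carry the extra condition that "the event rate is higher in the treatment arms than the placebo arm". The rule applies continuously: "Accrual will be temporarily suspended to this study if at any time we observe adverse events" of this kind. Neither limb contains a count or a comparison for a single dose.

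Section 13.2 randomizes "in a 2:2:1:1 ratio according to the dynamic allocation scheme". In expectation one third of men receive oxybutynin 5 mL, one third receive 2.5 mL, and one third receive placebo (the two placebo arms combined). Secondary objective 2.2.2 is "To characterize the safety and adverse event profile of two doses of oxybutynin in the study population". Section 13.4 summarizes grade 3 or higher events by arm and expects very few in any arm.

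Section 13.7.1 also allows discretion: "The study team may choose to suspend accrual because of unexpected adverse event profiles that have not crossed the specified rule below". It allows the rule to be changed during the trial. Section 13.7 has the DSMB review safety at least twice a year.

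**The concern.** The two active doses differ twofold, so dose-related toxicity is the pattern that a safety rule in this trial most needs to see. As written, the rule dilutes that pattern in two ways. The count is divided by all patients, two thirds of whom are not on 5 mL. The comparison then averages the 5 mL arm with the 2.5 mL arm before setting it against placebo. A high rate in one dose arm can therefore sit below the trigger while accrual to that arm continues. The plan gives no operating characteristics for the rule, so a reader cannot tell how much toxicity in one arm it would tolerate.

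**Working it through.** **Inputs.** Limit 10% of all patients, and 2 of the first 10 (13.7.1). Allocation 2:2:1:1 (13.2). 78 evaluable men plus a 10% allowance for loss gives 87 (13.5). The plan's figure reproduces: 78 / 0.9 = 86.7, rounded up to 87. The 5 mL arm then has 87 × 2/6 = 29 men, and the two oxybutynin arms together have 58.

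**Rate needed in the 5 mL arm.** With equal thirds, let x be the rate in the 5 mL arm and b the rate in each of the other two groups. The limit is met when (x + 2b)/3 = 10%, so x = 30% − 2b.

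- b = 0: 30%
- b = 2%: 26%
- b = 5%: 20%

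In whole patients, with events only in the 5 mL arm:

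- n = 30: 3 of 10 (30%)
- n = 48: 5 of 16 (31%)
- n = 60: 6 of 20 (30%)
- n = 78: 8 of 26 (31%)
- n = 87: 0.10 × 87 = 8.7, so 9 of 29 (31%)

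If the 9 events at n = 87 were spread over both doses, the pooled rate would be 9/58 = 15.5%.

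**The comparison condition can also block the rule.** Suppose 6 of 29 men on 5 mL, 0 of 29 on 2.5 mL and 3 of 29 on placebo are affected. The total is 9/87 = 10.3%, so the limit is met. Pooled oxybutynin is 6/58 = 10.3%, and placebo is 3/29 = 10.3%. The pooled rate is not higher, so the rule stays silent although the 5 mL arm is at 20.7%.

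**How often the rule is crossed.** Simulation of 87 men in blocks of six at 2:2:1:1, with events known at once and a check after every man. The early limb is kept, and the later limb runs from the eleventh man. The true rates are assumed; the documents give none. The per-arm columns replace the later limb by a limit within each oxybutynin arm, with at least 2 men affected and a rate above pooled placebo. Ranges reflect repeated runs.

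| True rate: 5 mL / 2.5 mL / placebo | Written rule | Per arm, 10% | Per arm, about 20% |
|---|---|---|---|
| 20 / 2 / 0% | 58–60% | 97% | 80% |
| 20 / 0 / 0% | 52% | not needed here | not needed here |
| 10 / 2 / 2% | 26% | about 70% | not needed here |
| 15 / 15 / 0% | 82% | not needed here | 83% |
| 2 / 2 / 2% (no drug effect) | 3.3–3.8% | 13% | 3.5% |
| 5 / 5 / 5% (no drug effect) | 20–22% | 48–49% | 19% |

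Most crossings of the written rule are chance crossings before full accrual. At a single look at n = 87, with a true 20% rate in the 5 mL arm and none elsewhere, the limit is met in 11% of trials; at a true 30% rate, in 52%.

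**The case against.** **Other safeguards exist.** Section 8.2 sets out steps for individual men, by dose. Section 11.6 provides weekly adverse-event calls, and Section 11.2 a weekly urinary symptom score. The study chair, the statistician and the DSMB review adverse events, and the team may pause accrual without the rule being crossed. This stands. A reader might infer that men on 5 mL have no protection until the rule fires, and the documents do not support that. The safeguards do not supply a numeric by-dose trigger, however. The discretion is worded for unexpected profiles, whereas Section 9.3.3 treats the events listed in Section 10 as expected.

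**The 30% is a worst case.** It is an observed rate with no events elsewhere. Background events lower it, and continuous checking lets lower true rates cross by chance. This also stands. It is wrong to read the rule as unable to fire below a true 30%.

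**A per-arm rule causes more false pauses.** At an unchanged 10% this is correct and substantial: about 48% instead of about 20% when every arm runs at 5%. At full accrual the 5 mL trigger falls from 9 men to 3 of 29, so part of the gain to 97% is simply a tighter limit. It is not all of the gain, as the calibrated column shows.

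**The rates are assumed.** Section 13.4 expects very few grade 3 or higher events, and Section 1.2 describes mostly mild effects. The crossing probabilities are therefore illustrative. The 30% − 2b relation does not depend on them.

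**The two limbs might seem to disagree at ten men.** A reader might infer that one event in ten satisfies the later limb but not the early one. The text does not establish this. The later limb starts after the first ten, which reads naturally as the eleventh man onward. There 10% of 11 is 1.1, so 2 events are needed and the limbs join. The simulated figures use that reading; with the later limb active at ten men, the written rule would be crossed in about 71% at 20 / 2 / 0%, not 59%.

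**Conclusion.** The concern holds for the numeric trigger in Section 13.7.1, not for safety oversight as a whole. Events confined to the 5 mL arm meet the limit only at an observed rate of about 30%, or 30% − 2b with a background rate b. Under idealized continuous checking and assumed rates, a true 20% rate crosses the rule in roughly 50–60% of trials, largely by early chance. Dose-specific counting is itself worth having. With the false-suspension rate held about equal, it raises detection at 20 / 2 / 0% from about 60% to 80%, and it loses nothing when both doses are equally affected (83% against 82% at 15 / 15 / 0%). The figures rest on an expected one-third share per group, immediate knowledge of events and a check after every man. Real reporting delays and uneven early allocation would shift them.

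**What to change.** In the second bullet of Section 13.7.1, assess events within each oxybutynin dose arm: men with a qualifying event divided by men treated in that arm, with at least 2 affected, compared with the pooled placebo rate. Keep placebo men out of the denominator.

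The sponsor should choose the per-arm percentage and state the false-suspension rate that it gives under one or two assumed background rates. The 10% should not be carried over by default, because that raises false suspensions from about 4% to 13% (2% in all arms) and from about 20% to 48% (5% in all arms). A limit near 20% shows that the current false-suspension rate can be kept; it is an illustration, not a recommended value.

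The cost is a wording change, a short simulation and one by-arm line in the DSMB report. No new data are needed. The rule already compares arms, so it already requires the assignments, and site blinding is unaffected. With a calibrated limit there is essentially no rise in unnecessary pauses, and any pause is temporary and affects accrual only.

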#### 3.2 Eligibility Criteria

Use the spaces provided to confirm a patient's eligibility by indicating Yes or No as appropriate. It is not required to complete or submit the following page(s).

When calculating days of tests and measurements, the day a test or measurement is done is considered Day 0. Therefore, if a test were done on a Monday, the Monday one week later would be considered Day 7.

- **3.2.1** Men who are currently receiving androgen deprivation therapy (ADT) for the treatment of prostate cancer. ADT is defined by a history of orchiectomy, or ongoing usage of gonadotropin-releasing hormone agonists or antagonists. Men receiving abiraterone, but not enzalutamide, apalutamide, and darolutamide are eligible, as the latter three are metabolized by CYP3A4 and may affect oxybutynin serum concentrations.
- **3.2.2** Patients must be on a stable dose of all hormone-directed therapies for at least 28 days prior to registration and must not be planning to discontinue this therapy for at least 42 days following registration.

Patients receiving radiation therapy during the study period are eligible.

- 3.2.3 Eligible patient must have bothersome hot flashes for  $\geq$  14 days prior to registration, defined by an occurrence of  $\geq$  28 times per week and of sufficient severity to cause the patient to seek therapeutic intervention.
- 3.2.4 No current use or future planned use of any of the following agents during the study period: drugs that are not FDA approved for use in humans, drugs with category X interactions with oxybutynin [e.g. other anti-cholinergic agents, eluoxadloline, and potassium chloride], androgens, estrogens, progesterone analogs, gabapentin, cholinergic agonists, cholinesterase inhibitors, or complementary/alternative medicine taken for the purpose of managing hot flashes. No current or future planned use of strong CYP3A4 inhibitors (e.g. antipsychotic agents or macrolide antibiotics) during the study.

Prior use of these agents is permitted as long as they are discontinued before registration.

3.2.5 No current or prior use of oxybutynin for the treatment of hot flashes. Prior use of oxybutynin for other purposes (e.g. bladder symptoms) is allowed, as long as the patient has not taken any oxybutynin for 30 days prior to registration.

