#### 9.2 CTCAE Routine Reporting Requirements

The following table outlines the combinations of time points, grades and attributions of AEs that require routine reporting to the Alliance Statistics and Data Center. Questions about routine reporting should be directed to the Data Manager.

Combinations of CTCAE Grade & Attribution Required for Routine AE Data Submission on Case Report Forms (CRFs)

Attribution	Grade 1	Grade 2	Grade 3	Grade 4	Grade 5
Unrelated			а	а	а
Unlikely			a	a	a
Possible		a	a, b	a, b	a, b
Probable		a	a, b	a, b	a, b
Definite		а	a, b	a, b	a, b

- a) Adverse Events: Other CRF Applies to AEs occurring between registration and within 30 days of the patient's last treatment date, or as part of the Clinical Follow-Up Phase.
- b) Adverse Events: Late CRF Applies to AEs occurring greater than 30 days after the patient's last treatment date.

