
Weekly hot flash frequencies (as opposed to weekly hot flash scores) will be compared across the oxybutynin and placebo arms in a manner similar to above using a mixed model that accounts for the observed distribution of weekly hot flash frequencies. A fixed sequence procedure will be employed. For the responder analysis, patients who experience a 50% or greater reduction in hot flash frequency since baseline will be deemed responders, while the remaining patients (including those with missing hot flash frequencies) will be deemed non-responders. Finally, consistency of the results will be assessed across the various methods used to evaluate the efficacy of oxybutynin in this trial (i.e., hot flash scores versus hot flash frequencies, mean differences versus 50% or greater reduction since baseline, single day versus full week to define patients' baseline hot flash scores).

**To assess safety**, the proportion of patients experiencing a grade 3 or higher adverse event will be summarized by arm. We expect this proportion to be extremely low for all arms.

To assess tolerability, mixed models similar to the one described above will be estimated that include baseline and weekly patient-reported symptoms as measured by the Symptom

Experience Questionnaire (Appendix V) across the 6-week treatment period. A single mixed model will be developed for each patient-reported symptom. Estimates from the mixed models will be used to construct 90% confidence intervals for mean differences in patient-reported symptoms between the oxybutynin and placebo arms (i.e., Arm A versus Arms C and D combined; Arm B versus Arms C and D combined) at 6 weeks post-randomization. Contrasts estimated via the mixed models will involve a two-sided *t*-test with a nominal significance level of  $\alpha = .10$ .

**To assess feasibility**, the time required to accrue 87 patients will be reported. To move forward with a phase III trial, an average accrual rate of 4 patients per month (starting 4 months after enrollment begins, to account for the time required for multiple institutions to activate the trial) would be desired. The treatment adherence rate (i.e., the number of patients who completed treatment per protocol divided by the number of patients who started treatment) will be summarized by arm.

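### The accrual-suspension rule counts related grade 3 events, but its pre-specified check of events filed as unrelated or unlikely covers only grades 4 and 5

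*Combined protocol and SAP*

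**What the plan says.** Section 13.7.1 (Adverse Event Stopping Rules) limits the rule to "adverse events considered at least possibly related to study treatment", meaning those recorded as possible, probable or definite. There are two triggers:

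- "if 2 or more patients in the first 10 treated patients experience a grade 3 or higher adverse event felt to be attributed", with oxybutynin or placebo as the cause;
- "if after the first 10 patients have been treated, 10% of all patients experience a grade 3 or higher adverse event" so attributed.

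Both also require a higher event rate in the treatment arms than in the placebo arm. Crossing either one suspends accrual temporarily. The section closes with a check on attribution: "We note that we will review grade 4 and 5 adverse events deemed" unrelated or unlikely. Its stated purpose is to verify the attribution and to pick up a related event that had not been recognized.

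Section 9.0 makes the site investigator responsible for attribution. The Section 9.2 table, headed "Combinations of CTCAE Grade & Attribution Required for Routine AE Data Submission on Case Report Forms (CRFs)", requires grade 3 events marked unrelated or unlikely to be submitted. On grade 3 or higher events by arm, Section 13.4 says: "We expect this proportion to be extremely low for all arms".

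**The concern.** The triggers and the safeguard do not cover the same grades. The triggers start at grade 3 and depend on the site's attribution. By providing a second look at attribution, the plan accepts that a site can get it wrong, but the second look starts at grade 4.

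Misfiling at grade 3 is plausible in this population. Section 10.1 lists urinary retention, constipation and drowsiness as effects of the drug. In men with prostate cancer each has other ready explanations, and Section 3.2.2 adds that "Patients receiving radiation therapy during the study period are eligible".

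The counts involved are small. Two men are enough in the first 10, and two are still enough up to the 20th man (10% of 20). If two of the first 10 men have a related grade 3 event and one is filed as unlikely, the count is one and the first trigger does not fire. At stake is whether a temporary suspension happens when the rule intends it. No efficacy estimate or test is affected.

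**Working it through.** **Stated figure.** The plan gives no operating characteristics for the rule, so there is nothing to reproduce. The calculation below only sizes the effect.

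**Inputs from the documents.** Triggers: Section 13.7.1. Allocation 2:2:1:1, which is 2:1 active to pooled placebo: Section 13.2. Maximum accrual 87: Section 13.5.

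**Assumptions, none of them in the documents.** p is the true rate of related grade 3 or higher events on oxybutynin. m is the share misfiled as unrelated or unlikely. All events are grade 3, none occurs on placebo (so the comparison between arms is always met), and a grade 3 review would correct every error.

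**Step 1: counted probability per enrolled man.** q = p × (2/3) × (1 − m). For p = 0.20, q is 0.1333 at m = 0, 0.12 at m = 0.10 and 0.0933 at m = 0.30.

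**Step 2: first-10 trigger.** P(X ≥ 2) = 1 − (1 − q)^10 − 10q(1 − q)^9. For p = 0.20 this gives 39% at m = 0, 34% at m = 0.10, 24% at m = 0.30 and 14% at m = 0.50.

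**Step 3: either trigger by 87 men.** The running count is followed man by man. The rule fires at a count of 2 within the first 10. From the 11th man it fires when the count reaches 10% of men so far: 2 for men 11 to 20, 3 for men 21 to 30, and so on up to 9 for men 81 to 87. Each man adds one to the count with probability q. An exact recursion gives:

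| True rate on oxybutynin | 0% misfiled | 10% misfiled | 30% misfiled |
|---|---|---|---|
| 5% | 17% | 14% | 9% |
| 10% | 52% | 45% | 30% |
| 15% | 82% | 75% | 56% |
| 20% | 95% | 92% | 77% |

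At a true rate of 3%, the chance is about 7% with no misfiling and 3% with 30% misfiled.

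**Step 4: sensitivity to the placebo rate.** A simulation with 2% related events on placebo, with the comparison between arms enforced, gives 86%, 78% and 64% for a 15% oxybutynin rate at 0%, 10% and 25% misfiled. The pattern does not depend on a zero placebo rate.

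**The case against.** The strongest reply is that these events are not hidden.

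- **Reporting.** Section 9.2 puts grade 3 events of any attribution on the routine form. Section 9.3.1 requires serious events to be reported whether or not they are thought related. Section 9.3.2 does the same for grade 3 events that lead to hospitalization.
- **Review.** Under Section 13.7 the study chairs and statistician review adverse events at regular intervals, and the DSMB reviews safety data at least twice a year. No grade or attribution limit is stated for either.
- **Discretion.** Section 13.7.1 lets the team suspend accrual before the rule is crossed and adjust the rule on new information.
- **Symptom tracking.** The weekly IPSS and the Symptom Experience Questionnaire record urinary difficulty, constipation and sleepiness without any attribution. Section 8.2 acts on severe urinary symptoms whatever their cause.

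A reader might infer from the closing sentence of 13.7.1 that a misfiled grade 3 event is never caught or its attribution never looked at. These provisions rule that reading out, because the events reach people who could question them.

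A narrower point remains. None of these layers states an attribution check for grade 3, or says that a corrected attribution counts toward a trigger. Timing matters as well. At the anticipated 7 patients a month (Section 13.6), 10 men accrue in about 10/7 = 1.4 months, while six months brings about 7 × 6 = 42. A twice-yearly DSMB review can therefore come after the first-10 window. The discretionary clause speaks of unexpected profiles, while Section 9.3.3 classes the Section 10.0 effects as expected, so it does not clearly reach them.

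The objections to the magnitude also stand. True rates of 15–20% and misfiling of 30% or more have no source in the documents, and the plan itself expects very few such events. Blinded sites may also over-attribute anticholinergic symptoms to the study drug, which would offset the loss and is not modelled. Full correction by review is an idealization. Limiting central review to the most severe events may have been deliberate.

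**Conclusion.** The mismatch is in the text. The triggers count grade 3 events attributed as at least possible, and the only pre-specified check of events filed below that level starts at grade 4. A misfiled grade 3 event drops out of both triggers unless general review happens to pick it up.

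The effect on the formal rule can be modest or large. With 10% misfiled, the chance of firing by 87 men falls by about 3 percentage points at a true rate of 5% (17% to 14%) and at 20% (95% to 92%), and by about 7 points at 10% and 15%. With 30% misfiled, the loss runs from about 8 points at a 5% rate to 26 points at 15%. These figures rest on the assumptions listed above and illustrate the mechanism; they do not predict what would happen in this trial. They describe the formal triggers alone, so they do not show that the trial's safety oversight as a whole would fail.

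This is a minor point, worth making because the remedy is cheap.

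**What to change.** In the last sentence of Section 13.7.1, replace grades 4 and 5 with grades 3, 4 and 5. Add that the attribution review is done blind to treatment arm, and that an event re-attributed as at least possible counts toward both triggers. If the team wants a smaller step, the addition could be limited to grade 3 events whose term is listed in Section 10.1.

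The cost is a sentence or two of text. The Section 9.2 form already collects the data, and a review of this kind already exists for grades 4 and 5. There would be a few more events to review, which the plan expects to be rare, and a slightly higher chance of a temporary suspension.
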